8.1.5.5 Dose Modification for Pembrolizumab

AEs associated with Pembrolizumab exposure may represent an immunologic etiology. These immune-related AEs (irAEs) may occur shortly after the first dose or several months after the last dose of Pembrolizumab treatment and may affect more than one body system simultaneously. Therefore, early recognition and initiation of treatment is critical to reduce complications. Based on existing clinical study data, most irAEs were reversible and could be managed with

Immune Design**G100 (GLA-SE) and Pembrolizumab or Rituximab****Protocol IMDZ-G142; Version 04B, November 15, 2018**

interruptions of Pembrolizumab, administration of corticosteroids and/or other supportive care. For suspected irAEs, ensure adequate evaluation to confirm etiology or exclude other causes. Additional procedures or tests such as bronchoscopy, endoscopy, skin biopsy may be included as part of the evaluation. Based on the severity of irAEs, withhold or permanently discontinue Pembrolizumab and administer corticosteroids. Dose modification and toxicity management guidelines for irAEs associated with Pembrolizumab are provided in [Table 3](#).

Immune Design**G100 (GLA-SE) and Pembrolizumab or Rituximab****Protocol IMDZ-G142; Version 04B, November 15, 2018****Table 3: Dose Modification and Toxicity Management Guidelines for Immune-related AEs Associated with Pembrolizumab**

General instructions:				

 1. Corticosteroid taper should be initiated upon AE improving to Grade 1 or less and continue to taper over at least 4 weeks. 2. For situations where Pembrolizumab has been withheld, Pembrolizumab can be resumed after AE has been reduced to Grade 1 or 0 and corticosteroid has been tapered. Pembrolizumab should be permanently discontinued if AE does not resolve within 12 weeks of last dose or corticosteroids cannot be reduced to ≤ 10 mg prednisone or equivalent per day within 12 weeks. 3. For severe and life-threatening irAEs, IV corticosteroid should be initiated first followed by oral steroid. Other immunosuppressive treatment should be initiated if irAEs cannot be controlled by corticosteroids. 				
Immune-related AEs	Toxicity grade or conditions (CTCAEv4.0)	Action taken to Pembrolizumab	irAE management with corticosteroid and/or other therapies	Monitor and follow-up

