### **5.7.2 Adverse Events**

A Treatment-Emergent Adverse Event (TEAE) is an AE with onset date on or after the initiation of study treatment, or a pre-existing condition that worsens after initiation of study treatment (i.e., increase in severity), up to 30 days after the date of last dose of study treatment. AEs that occur more than 30 days after last dose, if deemed as related to study treatment, will also be included as TEAEs.

If the AE start date is partial or missing, then:

- If AE start date is completely missing, then the AE is considered treatment-emergent.
- If both AE start month and day are missing, if the year is in the same year as the first study treatment, then the AE is considered treatment-emergent. Otherwise, 01Jan will be used to impute month and day. If the imputed AE start day is more than 30 days after the date of last study treatment, then the AE will not be a TEAE.
- If AE start day is missing and AE start year and month are the same or after the first dose year and month, then the AE is considered as treatment-emergent, unless the imputed AE start day using day 01 is more than 30 days after the date of last study drug.

The summaries will be based on TEAEs by part, treatment, and overall. A separate summary by treatment will be provided. All adverse events will be included in patient listings.

The incidence of a TEAE will be defined as the number and percent of patients experiencing an event. TEAEs will be summarized by system organ class, preferred term, and further by severity. Adverse events will be coded using Medical Dictionary for Regulatory Activities (MedDRA 20.1 or newer). A patient with more than one different adverse event in a system organ class (SOC) will be counted only once in the total number of patients experiencing adverse events in that particular SOC. A patient having experienced the same event (AE preferred term) more than once during the study will be counted only once under the worst grade or relationship.

The following adverse events summaries will be reported:

- Overall summary of TEAEs, including TEAEs, treated-related TEAEs, serious TEAEs, treatment-related serious TEAEs, TEAEs of grade 3 and above, treatment-related TEAEs of grade 3 and above, TEAEs leading to treatment interruption, TEAEs leading to treatment discontinuation, TEAEs leading to treatment interruption or discontinuation, TEAEs leading to death reported during the study, dose limiting toxicities (DLTs)

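### SAP 5.7.2 counts related adverse events beyond 30 days as treatment-emergent, but its partial-date rules exclude those whose imputed start falls beyond 30 days

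*SAP*

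**What the plan says.** SAP 5.7.2 sets the ordinary treatment-emergent window as onset or worsening from the start of study treatment "up to 30 days after the date of last dose of study treatment". It then extends the window for related events, with no upper time limit: "AEs that occur more than 30 days after last dose, if deemed as related to study treatment, will also be included as TEAEs".

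Three bullets follow for partial or missing start dates.

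- **No date at all:** "If AE start date is completely missing, then the AE is considered treatment-emergent".
- **Year only:** "if the year is in the same year as the first study treatment, then the AE is considered treatment-emergent". For any other year, "Otherwise, 01Jan will be used to impute month and day". A cut on timing then applies to that date: "If the imputed AE start day is more than 30 days after the date of last study treatment, then the AE will not" count as treatment-emergent.
- **Day missing:** an event in or after the month of first dose is treatment-emergent, "unless the imputed AE start day using day 01 is more than 30 days after the date of last study drug".

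The same section bases the AE summaries on TEAEs and puts all AEs in the patient listings. SAP 5.2 refers AE date imputation to the AE section, and neither document gives an exception for related events elsewhere.

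**The concern.** The definition and the date rules give different answers for the same event. The definition looks at relationship once an event is past 30 days. The year-only and day-missing rules do not. A late event that the investigator judged related can therefore be in or out of the tables according to how completely its start date was recorded.

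The tables at stake are the TEAE summaries in SAP 5.7.2. They include events related to study drug, to G100 and to pembrolizumab, the serious related events, and the related events leading to death.

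Late related events are foreseen. Protocol 8.1.5.5 says that immune-related events "may occur shortly after the first dose or several months after the last dose of Pembrolizumab treatment". Protocol 12.4 requires drug-related SAEs to be reported with no time limit. Such events can therefore reach the database long after day +30.

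**Working it through.** The plan gives no figure to reproduce. The check applies the rules literally to example dates.

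**Assumed dates, for illustration only:** first dose 6 November 2017, last dose 11 December 2017.

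**Days after last dose:**
- 11 to 31 December is 20 days, so 1 January 2018 is 20 + 1 = 21.
- 1 February 2018 is 20 + 31 + 1 = 52.
- 20 February 2018 is 20 + 31 + 20 = 71.
- 1 January 2019 is 21 + 365 = 386.

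| Start as recorded | Date used | Days after last dose | Related AE | Unrelated AE |
|---|---|---|---|---|
| 20 Feb 2018 | as recorded | 71 | TEAE | not TEAE |
| Feb 2018 | 1 Feb 2018 | 52 | **not TEAE** | not TEAE |
| Jan 2018 | 1 Jan 2018 | 21 | TEAE | TEAE |
| 2018 | 1 Jan 2018 | 21 | TEAE | TEAE |
| 2019 | 1 Jan 2019 | 386 | **not TEAE** | not TEAE |
| 2017 (year of first dose) | none needed | – | TEAE | TEAE |
| no date | none needed | – | TEAE | TEAE |

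The two bold cells contradict the definition. A related event on 20 February 2018 is a TEAE. Recorded as February 2018, it is not.

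**Uncertainty about the date does not explain this.** The first of the month and 1 January are the earliest dates that the partial date allows. If the earliest possible start is more than 30 days after last dose, the true start is too. So every related event that these clauses remove is one the definition includes.

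**Which events are exposed** (Protocol 12.4):
- For pembrolizumab patients, all AEs are required through 30 days after cessation. After that come SAEs to 90 days (or to 30 days if new anticancer therapy starts), and then drug-related SAEs only.
- For other patients, general collection runs to the end-of-study visit or 30 days after last dose, whichever is longer. In Parts 1 to 3, a G100-alone patient with a sixth and last dose on Day 35 and the visit on Day 77 has 77 − 35 = 42 days. Non-serious events between days +31 and +42 could then be affected. With a ninth dose on Day 56 the gap is 77 − 56 = 21 days, so no such interval arises.
- The exposed events are therefore mostly related SAEs.

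**Effect of one event on a table:**
- Part 2 arm of 12: 1/12 = 8.3 percentage points.
- Part 4 at its planned 22: 1/22 = 4.5 percentage points.

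These are maxima. SAP 5.7.2 counts patients, so overall related-event incidence moves only if that patient has no other related TEAE.

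**With an exception for related events added:** the two bold cells become TEAE, and every unrelated cell stays as it is.

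**The case against.** The strongest reply is that the sentence on late related events is general and governs the bullets. On that view the bullets only place an incomplete date inside or outside the 30-day window, and the related-event sentence still applies afterwards. A programmer could read it so. But the SAP does not say so, the year-only rule is an unconditional statement that the event is not a TEAE, and the bullets are the specific rule for these dates. Two competent programmers could build different flags.

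The second reply is that little would be hidden, and much of this stands. All AEs stay in the listings. Protocol 14.3.1 requires narratives for all SAEs and on-study deaths, and SAP 5.7.3 gives deaths their own table. Under Protocol 12.9 the DMC reviews related unexpected SAEs as they arise. What is affected is the count in the TEAE tables.

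A reader might also infer more than the documents support:

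- *That every late related event with an incomplete date is lost.* Events with no date, and year-only dates in the year of first treatment, still count.
- *That late events are the ones most likely to have partial dates.* Nothing in the documents shows this. Protocol 12.6 requires SAEs to be reported within 24 hours of awareness and obliges sites to supply follow-up information. Follow-up after progression every 8 to 12 weeks, by telephone or clinic visit, makes partial dates plausible but no more than that.
- *That the primary safety endpoint is affected in every part.* Part 1's endpoint stops at Study Day 28 (Protocol 5.4), the secondary safety endpoint stops 21 days after the G100 regimen (5.5), and DLTs are confined to the first 28 days (6.2).

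**Conclusion.** The point holds in limited form. Followed as written, the year-only and day-missing rules misclassify any related event whose partial date is imputed to more than 30 days after last dose, because the section's own definition counts it. This is an inconsistency between two current statements in SAP 5.7.2, not a missing detail.

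The likely effect is small. The documents give no frequency for such events, so the number affected cannot be estimated. The 8.3 and 4.5 points are per-event upper limits, and the second uses a planned size that may not have been reached, since SAP section 9 records that the sponsor terminated the study. The conclusion rests on a literal reading of the bullets and on late related events being entered with partial dates. It does not depend on the example dates.

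It is still worth correcting, because the tables affected are those for related and serious related events and the correction costs almost nothing.

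**What to change.** In SAP 5.7.2, make the exclusion in both the year-only and the day-missing bullet apply only if the imputed start is more than 30 days after last dose *and the AE is not assessed as related to study treatment*. Add the same condition to the TEAE flag in the ADaM specification.

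The cost is one clause in each bullet and one condition in the program. Unrelated events are classified as before, and no new data are needed because relationship is already recorded for each AE.

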### 5.7.3 Death

Deaths (and cause of death) will be provided in table and listing.

### 5.7.4 Clinical Laboratory Evaluation

Hematology and blood chemistry are assessed at baseline visit (Visit 2), Visit 10 and Visit 11. Urinalysis is assessed at baseline visit (Visit 2). Laboratory assessments included the following:

- Hematology: WBC with differential count, RBC count, hemoglobin, hematocrit, platelet count, PT, PTT and INR (PT, PTT and INR for baseline only)
- Serum chemistry: sodium, chloride, potassium, random glucose, blood urea nitrogen (BUN), creatinine, calcium, AST/SGOT, ALT/SGPT, total bilirubin, alkaline phosphatase, lactic acid dehydrogenase (LDH), total protein, albumin

- Urinalysis (baseline only): protein, glucose, blood, leukocytes, nitrites, urobilinogen, bilirubin, pH, specific gravity, ketones
- Thyroid function (Visit 2 (Parts 1-4), Visit 11 (Part 2 - Pembro arm), Visit 9 (Part 4), FU (Parts 1-4)): T3, T4 and TSH

All local laboratory data will be stored in the database with the units in which they are originally reported. Laboratory data in summary tables and patient data listings will be presented in the SI Units. Laboratory data not reported in SI units will be converted to SI units before further processing or data analysis.

Summary statistics (mean, median, standard deviation, and range) of laboratory values for hematology tests and chemistry tests and their changes from baseline values will be tabulated for each visit, by part, treatment, and overall. Baseline is defined as the last value prior to first study treatment dosing.

Laboratory tests will be graded using NCI-CTCAE v4.03 toxicity grading (see [Appendix 1](#)).

Worst change from baseline in toxicity grade for selected laboratory parameters will be presented in shift tables. For each patient, baseline grade will be cross-tabulated by the patient's maximum post-baseline grade. Data from both scheduled and unscheduled visits will be used for maximum post-baseline NCI-CTCAE grade of laboratory values.

All laboratory measurements will be presented in a listing.

### **5.7.5 Vital Signs**

Vital sign measurements include temperature, pulse (heart rate), respiratory rate, resting systolic and diastolic blood pressure, height and weight. Temperature, pulse (heart rate), respiratory rate, resting systolic and diastolic blood pressure will be collected from baseline visit (Visit 2) through end of study visit (Visit 12) and continued throughout follow-up visits. Height and weight will be collected at baseline visit only.

Summary statistics (mean, median, standard deviation, and range) of baseline and post-baseline vital signs measurements (temperature, pulse, respiratory rate, resting systolic and diastolic blood pressure), as well as the changes from baseline, will be tabulated for each visit, by part, treatment, and overall. Baseline is defined as the last value prior to first study treatment dosing.

All vital signs measurements will be presented in a listing. Clinically significant abnormalities in vital sign measurements will be flagged in listing.

### **5.7.6 Electrocardiogram (ECG)**

12-Lead ECG measurements collected in both scheduled and unscheduled visits will be presented in data listings.

### **5.7.7 Physical Examination**

Physical examination abnormalities will be included in the adverse event (abnormalities after the start of study drug) or medical history (abnormalities before the start of study drug) summaries and listings.

### **5.7.8 Pregnancy Test**

Pregnancy test results will be presented in a listing.

### **5.7.9 ECOG Performance Status**

ECOG performance status will be summarized by visit and presented in a listing.

### **5.7.10 Prior and Concomitant Medications**

Verbatim terms of prior and concomitant medications will be coded using the most current version of the World Health Organization (WHO) Drug Dictionary (3Q 2018 or newer).

All concomitant medications will be summarized by ATC class and preferred name and all prior and concomitant medications will be presented in a listing. A patient with more than one medication in a medication class will be counted only once in the total number of patients in that medication class. A patient having the same medication more than once during the study will be counted only once in the number of patients with that medication.

**Prior medication** is defined as any medication with start date on or before the first dose date, or medication with start date missing.

**Concomitant medication/treatment** will be any medication/treatment with start date on or after the initial dosing of study treatment. Any medication/treatment that cannot be identified as prior or concomitant will be considered as prior and concomitant.

Prior and concomitant medications will be presented in a listing.

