8.4.2 Prohibited Concomitant Therapy

The following treatments will be prohibited during study until the EOS visit or tumor progression:

- Any investigational drug other than G100, rituximab or pembrolizumab if enrolled on that study arm, is prohibited during the study
- Any systemic corticosteroid (including prednisone of any dose) within four weeks of first study treatment and during the study period (Intermittent use of inhaled or topical steroids is acceptable but chronic use or high doses where systemic absorption is expected should be discussed and approved by the Sponsor). For patients receiving pembrolizumab, systemic glucocorticoids may be used to modulate symptoms from an event of suspected immunologic etiology. However, the event should be discussed with the Medical Monitor before continuing therapy.
- Other concurrent immunosuppressive medications such as methotrexate, cyclosporine, azathioprine
- Concomitant chemotherapy, immunotherapy not specified in this protocol, or biologic therapy
- Except as given per protocol regimen, radiotherapy
- Anti-coagulation therapy – due to the increased risk of bleeding at the site of injection. Based on the consensus guidelines from the Cardiovascular and Interventional Radiology Society of Europe, if a patient is to have a superficial lymph node or subcutaneous mass injected, NSAIDs, aspirin, or clopidogrel may be used and do not have to be withheld ([Patel 2012](#); [Patel 2013](#)). For procedures with moderate or significant risk of bleeding, long-acting agents such as aspirin or clopidogrel should be discussed with the Medical Monitor and may need to be discontinued before beginning G100 therapy.
- Live vaccines within 30 days prior to the first dose of study treatment and while participating in the study. Examples of live vaccines include, but are not limited to, the following: measles, mumps, rubella, varicella/zoster, yellow fever, rabies, BCG, and typhoid vaccine. Seasonal influenza vaccines for injection are generally killed virus vaccines and are allowed; however, intranasal influenza vaccines (e.g., FluMist®) are live attenuated vaccines and are not allowed.

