8.4.3 Permitted Concomitant Therapy

The following medications will be permitted:

- Antihistamines
- Anti-emetics
- Anti-diarrheals
- If a patient is to have a superficial lymph node or subcutaneous mass injected, NSAIDs, aspirin, or clopidogrel are acceptable and do not have to be withheld. For procedures with moderate or significant risk of bleeding, long-acting agents such as aspirin or clopidogrel should be discussed with the Medical Monitor and may need to be discontinued before G100 therapy.

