## **5.2 Missing Data**

For adverse events and concomitant medication, the imputation rule for start date and end date are defined in relevant sections (i.e., AE and subsequent therapies sections). For other analysis when necessary (e.g., OS analysis), dates without a specific day of the month (i.e., JAN2010) will be assigned the 15th day of the month and dates without a specific day or month (i.e., 2010) will be assigned the 15th day of June.

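### SAP 5.7.10 defines concomitant medication by start date alone, so permitted drugs begun before first dose and continued on study are left out of the summary table

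*SAP*

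**What the plan says.** SAP 5.7.10 gives two definitions and a fallback. Prior medication "is defined as any medication with start date on or before the first dose date, or medication with start date missing". Concomitant medication "will be any medication/treatment with start date on or after the initial dosing of study treatment". The fallback reads: "Any medication/treatment that cannot be identified as prior or concomitant will be considered as prior and concomitant".

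The outputs differ between the two classes: "All concomitant medications will be summarized by ATC class and preferred name and all prior and concomitant medications will be presented in a listing". No summary table is planned for prior medications. Prior anti-cancer therapy has its own summary in SAP 5.5.4, but other prior drugs do not.

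On dates, SAP 5.2 states: "For adverse events and concomitant medication, the imputation rule for start date and end date are defined in relevant sections". It points to the adverse event and subsequent therapy sections.

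The protocol treats concomitant therapy as a matter of use during the study. Section 8.4.2 prohibits certain drugs until the end-of-study visit or tumor progression. Section 8.4.3 lists what may be taken; for injection of a superficial node or subcutaneous mass, "NSAIDs, aspirin, or clopidogrel are acceptable and do not have to be withheld".

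**The concern.** A drug begun before first dose and still being taken is concomitant in the ordinary sense and in the protocol's sense. Under the SAP rule it is only prior, and prior drugs are not tabulated. A reader would take the ATC table as on-study drug use, when it shows only drugs started on or after the first dosing day.

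What is at stake is how complete one descriptive safety table is. Long-standing drugs are the ones most likely to have been started before entry. Some of them matter when safety is read: Protocol 8.4.2 itself links aspirin and clopidogrel to bleeding after intratumoral injection, and thyroid or diabetes replacement at baseline is useful context for endocrine events in patients on pembrolizumab.

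**Working it through.** No figure in the plan is in question and no arithmetic applies. The check is to apply the SAP 5.7.10 wording to each pattern of start and stop dates.

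| Pattern | Class under SAP 5.7.10 | In ATC table? |
|---|---|---|
| Started and stopped before first dose | Prior | No (correct) |
| Known start before first dose, continued on study | Prior only | No |
| Started on the day of first dose | Meets both definitions | Yes |
| Started after first dose | Concomitant | Yes |
| Start date missing | Prior by definition | Unclear (see below) |

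The second row is the problem. Three places might have repaired it.

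1. **The fallback sentence.** It applies only when a drug cannot be identified as prior or concomitant. A known pre-dose start identifies the drug as prior, so the fallback is not reached. A missing start date is also prior by definition, which undercuts what seems to be the fallback's purpose. What it can still reach is a partial start date that straddles first dose.
2. **SAP 5.2.** The sections it points to are 5.7.2, which deals with adverse event start dates, and 5.6.7, which deals with subsequent anti-cancer therapy dates. Neither gives a rule for concomitant medication, and neither adds a criterion of ongoing use.
3. **The protocol.** The visit procedures record previous and concomitant medications together and do not define the split.

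Next, which drugs fall in the second row. From Protocol 7.2 and 8.4:

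- **Allowed to continue:** NSAIDs, aspirin and clopidogrel for superficial injections (exclusion 14, 8.4.2, 8.4.3), and replacement therapy for hypothyroidism or diabetes (exclusion 11). In an eligible patient these are typically started before entry and carried on, so the rule under-counts them.
- **Barred at entry:** systemic corticosteroids and other immunosuppressants (exclusion 5) and anticoagulants (exclusion 14). Section 8.4.2 also bars them on study; for corticosteroids the bar covers "Any systemic corticosteroid (including prednisone of any dose) within four weeks of first study treatment and during the study period". An eligible, compliant patient has no such use to carry over.
- **Corticosteroids allowed on study:** systemic glucocorticoids for a suspected immune event in patients on pembrolizumab. These would normally start after first dose, so the rule captures them.

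For any drug, the table's shortfall is the number of patients whose only use of it began before first dose and continued. The documents give no counts from which to estimate this.

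**The case against.** The best reply is that little depends on this table. The listing keeps every drug, so nothing is lost from the record. The population definitions (SAP 4.1 to 4.3) do not mention the prior/concomitant flag. PFS censoring (SAP 5.6.4) turns on new anti-cancer therapy, radiotherapy or surgery, not on this classification. The analyses are descriptive or exploratory, and SAP section 9 records that the sponsor terminated the study. All of that stands, and it sets the severity.

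A reader might also infer something stronger: that the rule hides chronic use of corticosteroids, immunosuppressants and anticoagulants, and that this table is the only summary of restricted drugs. The documents do not support that. Those classes are excluded at entry and prohibited on study, so pre-dose use that continues is a deviation. SAP 5.4 has the study team review all potential deviations at intervals and before database lock, and tabulates the CSR-reportable ones by type. That table need not name the drug, and the ATC table would miss a prohibited drug continued in error, but the use would have another route into the report.

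Nor is every chronic drug misfiled. One that starts on the day of first dose meets both definitions and is tabulated.

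None of this answers the narrower point: permitted drugs carried over from before first dose are left out of a table presented as concomitant use.

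**Conclusion.** The point holds in limited form. As written, SAP 5.7.10 leaves out of its only planned concomitant-medication table any drug with a known pre-dose start that continues on study. The main effect is on permitted antiplatelet drugs, NSAIDs, and thyroid or diabetes replacement. It is a wrong rule rather than a missing detail, and correcting it would change the reported counts wherever such use occurred.

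The severity is low. The effect is confined to one descriptive table, the listing is complete, and no endpoint or population definition refers to the flag. The number of patients cannot be derived from the documents. The conclusion assumes that the definitions will be programmed as worded and that some patients enter on a permitted long-term drug, which the protocol allows but does not quantify.

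**What to change.** Replace the definitions in SAP 5.7.10 along these lines:

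- **Concomitant:** any medication taken on or after first dose of study treatment. That means it started on or after first dose, or it started earlier (or has a missing start date) and is either ongoing or stopped on or after first dose.
- **Prior:** any medication started before first dose. A drug may be both prior and concomitant.
- **Missing dates:** count the drug as concomitant unless its stop date is before first dose. This replaces both the missing-start clause under prior and the present fallback.

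Use one anchor date throughout. It is first dose of study treatment, which should not be assumed to be Day 0: in Parts 1 to 3 the first G100 injection is on Day 2, after radiation on Days 0 and 1. The SAP 5.2 cross-reference should then point to 5.7.10 for medication dates.

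The cost is a few sentences and one derived flag in the analysis dataset. No new data should be needed, on the assumption that the case report form holds stop dates or ongoing status; SAP 5.2 implies this by referring to end dates for concomitant medication.
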